Maternity care has been hard-hit by increasingly complex medical and social comorbidities in pregnancy over the past decade,¹ exacerbated by increased substance use in pregnancy, a widening gap in socioeconomic inequities, and the deep impact made by the COVID-19 pandemic on vulnerable populations.² We have seen an increase in maternal mortality, and while advancing maternal age is a major risk factor, socioeconomic disadvantage is equally deleterious.³ Traditional single-care-provider models have not adapted to address the complex care needs of the 21st century⁴ with current research being dominated by provider perspectives rather than patient perspectives and experiences.⁵ This gap in the literature is troubling as the patient voice is essential to the ethical design of more responsible care strategies. As a former Canadian Child Health Clinician Scientist Program (CCHCSP) Career Development Award recipient and first Canadian Clinician Midwife, I focused on the development of an innovative interprofessional model of maternity care to improve perinatal outcomes in pregnant persons with complex care needs. As a result of the CCHCSP training and support, I successfully co-developed an interprofessional team of maternity care providers, who have a unique approach to address the complex care that persons need during pregnancy, birth, and postpartum. This *Interprofessional Psychosocial Perinatal Care Clinic* (IPPCC) team features obstetrics, midwifery, psychiatry, and opioid agonist therapy access within a dedicated team of shared-care providers who offer clinic, virtual, and home/shelter based-care to pregnant persons at high psychosocial risk. We have aligned our care approach with the World Health Organization's international guiding principles for the management of substance use in pregnancy, which include prioritized prevention, access to prevention and treatment services, respect autonomy, comprehensive care, and safeguard against stigma.⁶ Our team seeks to advance the interprofessional care approach and research by trialing Dialectical Behaviour Therapy (DBT) skills, based on [name] DBT skills group outlines⁷, and then to inform content by Indigenous knowledge from the Elder on our team. Therefore, the primary goal for this project is to conduct interviews (pre/post DBT skills session) with patients who agree to participate in Perinatal DBT skills sessions with an interprofessional team which will guide our care approach with equity-deserving populations and future clinical research priorities.

Many persons who are Indigenous, newcomers, underhoused, suffering substance use disorders and those who experience mental health conditions have significant barriers in accessing health care.⁸⁻¹⁰ Most notably

persons may not seek care due to stigma, systemic marginalization, structural racism, concern for criminal consequences, and fear of child apprehension.¹⁰ To understand more about substance use in pregnancy and patient-centred care approaches, we conducted a scoping review and found no published evidence of an interprofessional maternity care model that was informed by the voice of pregnant persons who use substances.¹¹ Furthermore, we did not find any evidence of best practice guidelines that were comprehensive and actionable; most guidelines cited broad, generic clinical recommendations.¹¹ Our proposal aims to fill these knowledge gaps and centre the patient's voice in our clinical model.

Dialectical Behaviour Therapy skills interventions have been shown to improve depression, anxiety, anger control, and emotional regulation^{7,12-13} We plan to modify DBT based on feedback from the Elder's experience co-leadership in the sessions, and the patient's experience. The team members from the interprofessional team who will guide the sessions are, Psychiatry-lead, Social Work, and Elder.

Hypothesis and Outcomes

There are 2 outcomes of interest related to our work with our patients: 1) Evaluate the impact of the perinatal DBT skills sessions in patients with complex care needs 2) Adapt DBT to ensure cultural safety throughout the process. Ultimately these outcomes will inform our research priorities and care approach. We expect the care outcomes to align with constructs reflected in our team's *Interprofessional Psychosocial Perinatal Care Framework* juxtaposed with the *Valuing All Voices Framework* (Appendix A).

Project Design, Framework, and Specific Aims

Project Design: Our project design involves the development of Perinatal DBT. We will follow patient-engagement strategies as delineated by the Centre for Healthcare Innovation. Specifically, we will adopt the *Valuing All Voices Framework* to guide our work with the vulnerable population we serve.¹⁴ This framework encompasses five key concepts with definitions that will guide our work: 1) Education and Communication, 2) Understanding and Acceptance, 3) Trust, 4) Relationship Building, and 5) Self-Awareness. In 2021, our interprofessional clinical team created a framework to guide our clinical care approach. Our framework is based on an integrated psychosocial perinatal care model that we practice and delineates three domains: Social, psychological, and perinatal. Each domain intersects and describes aspects of interprofessional engagement to consider when tailoring care for each person with complex needs. Birth experience is at the centre of these domains. Examples of our IPPC model that we offer are reflected in the intersecting domains and are as follows but not limited to social supports, housing, food safety, meaningful employment, neurodiversity health, gender identity, trauma informed care and support, addictions treatment, coping skills, cultural supports, self-care, parenting tools, grief counselling, perinatal psychiatric care, emancipation from domestic violence, and others (Appendix A). Finally, in adopting and considering the *Valuing all Voices Framework*, we will evolve our approach to patient-informed care, and it will support and guide us to use a health equity and a social justice lens to guide our patient-engaged approach.

The purpose of this study is to understand if an adaptation of the standard DBT is culturally safe. We have engaged and invited an Indigenous Elder to co-lead and inform the adaptation of DBT.

Specific Aim 1: To evaluate patient feedback from evidence informed adapted DBT in the context of complex care patients.

Specific Aim 2: To understand patient perspectives of the DBT skills sessions with the participation of an Elder.

Experimental Methods of Engagement

With patient engaged research, various participatory approaches and engagement methods can be considered at different stages in the research process. We are utilizing an evidenced informed method of DBT skills and adapting it to include leadership from an Indigenous Elder. This process will be reciprocal, and flexible regarding the protocol to ensure a culturally safe environment. We will utilize the Methods for Patient and

Public Engagement Guide to map our research stage, level, and method of engagement.¹⁵ These stages include preparing for execution, data collection, data analysis, dissemination, implementation, and evaluation. Within each of these stages there are various engagement levels (consult, collaborate and partner representative) and then various methods of engagement (appreciative inquiry, discussion groups, interviews, etc.). With this stepwise approach, we will identify outcomes-measures that are meaningful to the population served while maintaining study rigour.

Population: Complex care persons with lived experience of psychosocial comorbidities in pregnancy experience systemic barriers to accessing comprehensive maternity care. Patients will have engaged in care in the *Interprofessional Psychosocial Perinatal Care* clinic from October 2023-June 2024 (9 months). We anticipate 6 to 8 persons per cycle, up to a maximum of 15 persons per cycle. We anticipate running 6 cycles over 9 months. We hope to interview approximately 40-50 patients during this 9-month period. This clinic has a minority Caucasian population, with most patients living on social assistance or with homelessness, and an overrepresentation of criminal justice and/or child protection agency involvement, with approximately 75% of patients identify as Indigenous (First Nations), Métis, and/or Inuit. Our research team has significant experience in collaborating respectfully with and servicing Indigenous patients and communities. The Elder will be the Indigenous lead and understanding as we undertake this project in a good way with the patients.

Recruitment: Using the Patient Recruitment Script postcard we will seek permission to contact persons to participate in interviews related to the DBT skills sessions. The psychosocial obstetrician and the perinatal psychiatrist will engage potential patients to identify if they might have an interest in participating in a pre and post session interviews. **Inclusion criteria:** Patients who have their own agency and decision-making power over their health care. Patients may be antepartum or postpartum at the time of patient invitation. We will not engage minors, nor will we engage a patient who is psychologically or physically unstable. Our patient population in this clinic is very diverse and includes Black, Indigenous, and People of Color (BIPOC). **Exclusion criteria:** Patients who are minors or who are psychologically or physically unstable. Our team of clinicians will screen patients prior to any initiation of engagement with these inclusion criteria as our guide, and a Pledge of Confidentiality will be obtained.

Timeline: October 2023-June 2024 (9 months). There are 6 sessions that will rotate on a weekly basis throughout the 9 months. The 6 sessions make up one cycle. The DBT skills sessions will be run the first three Thursdays of every month.

Setting: *Interprofessional Psychosocial Perinatal Care* clinic (Green Leaf) in the Ambulatory Care Clinic at Health Sciences Centre, Women's Hospital.

Interprofessional Psychosocial Perinatal Care (IPPC) team composition: Psychosocial Obstetrician with expertise in substance use and mental health issues during pregnancy; Midwife clinician scientist, Perinatal Psychiatrist with capacity for mobile care; Indigenous Elder, and Social Work with hospital-based and outpatient capacities. These individuals comprise the dedicated team of shared-care providers who offer in-patient, clinic, virtual, and home/shelter-based care to pregnant persons at high psychosocial risk with complex care needs and liaise with care-partners such as Infectious Disease, Cardiology and Outreach Nursing on a case-by-case basis. Community programs such as Nine Circles, Klinic Mobile Withdrawal, the Mothering Project and Ka Ni Kanichihk provide reciprocal referral pathways. Only the Psychosocial Obstetrician and the midwife clinician scientist, however, will be involved in the recruitment via the patient engaged activities we have delineated in our project, as they have the primary relationship with all IPPCC patients.

Data Collection: Pre and post session Interviews and Appreciative Inquiry (see data analysis stage) will be the two methods of engagement. The purpose of the qualitative pre and post session interviews is to glean an understanding of what the patients understanding of the benefit of DBT and their needs and then to

understand how DBT impacted health and well-being at the end of the DBT skills session. Our team will use a semi-structured interview guide for the pre-interviews and develop the post interview guide towards the end of the nine months. The post interview guide will be informed by what we learn and feedback from the Elder throughout this process and from the pre-interview data. Our IPPC team supports 35 to 40 patients during any given month, with deliveries balanced by new intakes. Our end goal is to have 8 to 10 patients participate in DBT skills sessions, with a maximum of 15 per cycle.

During our pre and post interviews we will gather qualitative data to articulate patient care priorities and to understand the impact of the DBT skills sessions. We anticipate each interview to be approximately one hour in a neutral space provided at HSC. Because these patients are under our care, we will provide continual support throughout the process in terms of mental health supports and other supports.

We will also use Appreciative Inquiry to guide our reflection in our team outside of our patient engagement processes. Therefore, another point of data collection for this project will entail an IPPC team meeting at 6 months and 12 months to reflect on our understanding, interpretation, and analysis from our engagement with patients. We will have an Appreciative Inquiry facilitator lead our team meetings to ensure reflexive practice amongst our IPPC team throughout the time of this project.

Data Analysis

As we engage patients to gain an understanding of patient experience and impact of DBT skills sessions, we will use a *collaborative* Appreciative Inquiry approach in these dialogues (i.e., interviews). Appreciative inquiry (AI)¹⁶ is a strengths-based approach that identifies optimal care experiences to define care strategies that are successful from a patient perspective; it begins with “what works” rather than staying mired in “what doesn’t.” Additionally, AI identifies patient strengths to provide a conceptual scaffold upon which to build a care model grounded in lived experience and will use this approach to analyze the client interviews. This method of engagement will guide our interprofessional clinical team to ensure we employ reflexive practice, explore patient expectations, and respect and hear the patient’s voice in research design and development to improve their care experiences. This design partnership supports positive change among the clinical team members and facilitate true interprofessional work, and ultimately ensure the patient is at the centre of our care delivery and team.

In analyzing the data from the pre and post interviews, we will complete a content analysis from the recorded interviews. We will all code the data and come together to cross-check and validate our interpretations of this experience via the Appreciative Inquiry process at one of our clinical team meetings without patients involved. This will ensure we have an opportunity as a clinical team to reflect on process. Our patients will have the opportunity to review the transcribed interviews and the analysis by the team to ensure accuracy of their perspectives.

All our analyses from this project will be an iterative process as we go back and forth to both the IPPC the Valuing All Voices Frameworks (Appendix A) to analyze and validate our findings in relation to the constructs reflected in each. We will adapt DBT based on the feedback and insight from the patients.

Safety and Risk

We anticipate low potential risks and discomforts in this project. Patients will be asked about their experiences surrounding DBT skills sessions offered by the Interprofessional Psychosocial Perinatal Care team which could bring up past trauma and discomfort. The care team will support patients who participate in DBT skills sessions and will offer the services of the clinic's perinatal psychiatrist if the patient chooses. An Indigenous Elder will be available to speak with patient if they choose. Because these patients are under our care, we will provide continual support throughout the process in terms of mental health supports and other supports. The PI or [name] will follow up with the affected patient at an appropriate time.

[name], [name], and [name] will meet every month to discuss the progress and safety of the project. All adverse events and unanticipated problems will be resolved immediately after the event and Shared Health Impact will be notified.

Privacy

The Patient names and other identifying information will only be captured on the Patient Recruitment postcard and the Pledge of Confidentiality. These documents will be uploaded to a secure server at the University of Manitoba (UM) by the research coordinator (RC) and only the PI and RC will have access to the folder. The hard copies of the documents will be stored in a locked filing cabinet in the PI's locked office at the University of employment, which only the PI has access to that filing cabinet. The audio-recording will not contain identifying information but rather the patient's assigned code.

[name] work computer is password protected and the passwords are only known by the individual's whose computer it belongs to. Any confidential information that needs to be printed and stored will be placed in a locked cabinet in the RC's office, which is accessed through a locked door.

The audio-recordings and digital files will be deleted from the UM server and DataVerse. All physical data will be confidentially shredded and discarded.

The data will be stored for 7 years.

Outcomes and Knowledge Translation

Anticipated outcomes: We anticipate we will garner new knowledge from the patient pre/post interviews. And from this we can adapt DBT to ensure it is culturally safe. We are planning research priorities and future grant development and will include this process.

Knowledge Translation: Our team keeps health equity as the focal point of every study. To understand the effects of interventions on health equity for the populations we serve, an iterative process of analysis, synthesis, and ethical knowledge dissemination and application will be executed alongside decision makers and patients involved. We hope to discuss this experience and findings at obstetrical rounds and national forums. Our KT plan will also be informed with engagement of our Indigenous research team members. Additionally, we would publish in peer reviewed journals.

Anticipated Barriers: We anticipate logistical barriers with the patients, which can include transportation, childcare, and transient housing. There are also systemic barriers such as power inequities, lack of trust in the health care system, and the colonization that is represented in institutional environments. Mitigation: We will support travel and honorariums for each of the patients who are involved. We will provide the following with the support of this grant to encourage patient attendance at meetings: 1) Taxi slips there and back, and 2) snack food and drinks (and let them know ahead of time this is provided). We will collaborate with our patients to ensure meeting spaces feel safe and times are convenient. Practicalities like childcare and COVID-19 protocols will be addressed. The Indigenous Elder will give guidance throughout this project to ensure our

care approaches reflect the priorities of Truth and Reconciliation, coming to this work from a place of humility and willingness to learn.

External readiness: Our team has experience working in Manitoba communities in dual roles as both researchers and clinical providers. We know from our clinical experiences and the literature that persons want to be self-directed in their health care particularly in pregnancy, persons desire choice and culturally safe care.¹⁷ We also know many persons welcome opportunities to debrief and process the maternity care they have received whether it was a good or bad experience. Across all cultures new parents process their birth experience through storytelling as part of their transition into parenthood.¹⁸ This study will not only create an opportunity for this type of sharing but will keep it at the heart of maternity care development.¹⁹

Significance of the Research

My innovative overall research program, *Pathways to Care*, aims to improve maternity care delivery for complex care persons by implementing innovative care models, that create seamless pathways to care. This project will advance intervention research with our clinical team that was established during the tenure of the CCHSP award. Our objective is uniquely grounded in patient-identified priorities, Indigenous wellness values, and collaborative care models; these interventions intersect and are the basis to my *Pathways to Care* research program. For this project as we accomplish our three outcomes, we will then work towards with future funding initiatives (see Future Research Directions section).

The patient perspective from this work will inform how we will define and measure outcomes in this patient population. We will budget in future grants funding to support ongoing resources for DBT skills sessions as a regular part of this care model. We expect this care model will support maternity care providers struggling to support complex populations with actionable strategies that align with patient goals. We expect to demonstrate the impact of an innovative interprofessional team to champion the care needs of marginalized pregnant persons without additional system resources. My overall research program addresses issues of equity and access at the root of the problem and includes disadvantaged voices at every level of my research. My work alongside patients, provincial and national policy makers, and Northern decision makers aligns with and impacts healthcare transformation priorities, such as integration, efficiencies, adaptability, equity, and quality.

Future Research Directions (including likely future sources of support)

At the end of this project, we will have the perinatal DBT skills integrated into our research initiatives in the *Interprofessional Psychosocial Perinatal Care Clinic*. We will engage patients from the outset to have them inform our process and direction for a larger CIHR grant. We hope the information generated from the patient voice will inform how to improve patient care processes and delivery in our clinics that serve diverse populations.

Forms/Information

- Pledge of Confidentiality
- Patient Recruitment postcard
- SOPs (Standard Operating Procedure)

References

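### Six cycles in nine months do not fit a three-Thursday calendar, which gives 27 sessions (4.5 cycles), and the number of participants is stated two ways

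*Protocol*

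**What the plan says.** Three paragraphs of the Protocol, all under Experimental Methods of Engagement, bear on this point.

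- **Population** gives the number of cycles, "We anticipate running 6 cycles over 9 months", the group size, "We anticipate 6 to 8 persons per cycle, up to a maximum of 15 persons per cycle", and the total, "We hope to interview approximately 40-50 patients during this 9-month period".
- **Timeline** sets the window at nine months, October 2023 to June 2024. It continues: "There are 6 sessions that will rotate on a weekly basis throughout the 9 months. The 6 sessions make up one cycle". It then fixes the days: "The DBT skills sessions will be run the first three Thursdays of every month".
- **Data Collection** gives a second participation figure: "Our end goal is to have 8 to 10 patients participate in DBT skills sessions, with a maximum of 15 per cycle".

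The Protocol does not show how the cycle count or the interview total was derived.

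**The concern.** The number of cycles follows directly from the length of the window, the sessions per month and the sessions per cycle. The Protocol states all three, and they do not give six. The group size appears as two different ranges, and the second does not say what it counts. The expected number of interviewed patients presumably depends on both quantities, so a reader cannot trace it to the plan.

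No hypothesis test or power calculation depends on these figures. At stake are whether the hoped-for number of interviews is realistic, how much Elder, psychiatry and social work time is committed, and the budget for honoraria and taxi slips. There is also a data question. The post-session interview is meant to capture the effect once the sessions have ended, so it matters whether patients in an unfinished cycle are counted.

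**Working it through.** **Inputs**

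- Window: 9 months, October 2023 to June 2024 (Timeline)
- Sessions per cycle: 6 (Timeline)
- Sessions per month: 3 (Timeline)
- Stated cycles: 6 (Population)
- Persons per cycle: 6 to 8, ceiling 15 (Population)
- Participants, second statement: 8 to 10, ceiling 15 per cycle (Data Collection)
- Interviews hoped for: about 40 to 50 (Population)

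**Step 1. Can the stated six cycles be reproduced?** Cycles = sessions available ÷ 6.

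- Three Thursdays a month: 9 × 3 = 27 sessions; 27 ÷ 6 = 4.5 cycles. By the calendar, the fourth cycle ends on 16 May 2024, and the fifth has had three sessions when the last date, 20 June 2024, is reached.
- Every Thursday in the window: 39 sessions; 39 ÷ 6 = 6.5 cycles, six of them complete.

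Six cycles come out only if the weekly rotation means a session every Thursday, and the three-Thursday sentence in the same paragraph excludes that.

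**Step 2. Size of the gap.** Six cycles need 6 × 6 = 36 sessions. At three a month that is 36 ÷ 3 = 12 months. Shortfall: 36 − 27 = 9 sessions; 9 ÷ 36 = 25%.

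**Step 3. Expected patients.** Patients = cycles × persons per cycle. This assumes that each patient is counted in one cycle and that every participant is interviewed. The Protocol states neither.

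| Cycles | At 6–8 | At 8–10 | At ceiling 15 |
|---|---|---|---|
| 4 (complete) | 24–32 | 32–40 | 60 |
| 4.5 (half cycle pro rata) | 27–36 | 36–45 | 67.5 |
| 5 (unfinished cycle counted as a full group) | 30–40 | 40–50 | 75 |
| 6 (as stated) | 36–48 | 48–60 | 90 |

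Comparing low end with 40 and high end with 50, at 6 to 8 per cycle:

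- Four cycles: 1 − 24/40 = 40% and 1 − 32/50 = 36% below.
- 4.5 cycles: 1 − 27/40 = 32.5% and 1 − 36/50 = 28% below.

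At 8 to 10 per cycle the same comparison gives 20% below (four cycles) and 10% below (4.5 cycles). Those ranges are not wholly under the target: 32–40 touches it at 40, and 36–45 overlaps it from 40 to 45.

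**Step 4. What 40 to 50 would require.**

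- Four cycles: 40/4 = 10 to 50/4 = 12.5 per cycle.
- 4.5 cycles: 40/4.5 = 8.9 to 50/4.5 = 11.1 per cycle.

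Both are above the anticipated 6 to 8 and below the ceiling of 15.

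**Step 5. Where 40 to 50 might come from.** Six cycles at 6 to 8 give 36–48, which is close. Five at 8 to 10 give exactly 40–50. Either link is inference.

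**Step 6. The two participation figures.** If 8 to 10 is per cycle, it shares only the value 8 with 6 to 8. If it is a study total, it cannot yield 40 to 50 interviews on any calendar, because the Protocol's opening paragraph describes the interviewees as patients who take part in the sessions.

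**The case against.** The best defence accepts the session count and disputes what is built on it.

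- **The weekly rotation may describe content only**, with a different session each week that one is held. The Timeline paragraph is then consistent with itself. This is a fair reading, but it fixes the calendar at 27 sessions and leaves the conflict with six cycles intact.
- **The 6 to 8 is an expectation and the 8 to 10 a goal**, and the two can coexist. The ceiling of 15 is the same in both places, and a study total of 8 to 10 is the less likely reading, since that sentence ends with a per-cycle ceiling. This softens the second conflict to an ambiguity, but the text still does not say which figure to plan on or what the second one counts.
- **Cycles times persons is only one model of recruitment.** Rolling entry could change the number of people reached, and the Protocol does not say that groups are closed. It does not describe rolling entry either. The patient totals are therefore conditional, whereas the session count is not.
- **The cycle, group-size and interview figures are hedged, and the study is qualitative.** Hedging excuses departures from a plan but does not make the plan agree with itself. The calendar and the definition of a cycle are stated without hedging. The qualitative design does limit the consequence, as does the ceiling of 15, under which 40 to 50 remains possible.

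**Conclusion.** The concern holds. By the Protocol's own definition and calendar, nine months contain 27 sessions, which is 4.5 cycles with four complete, not six. The gap is 9 sessions out of 36, or 25%. This part rests on stated figures alone.

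The effect on patient numbers is conditional on one cycle per patient and an interview for every participant. At the anticipated 6 to 8 per cycle, the calendar gives 24–32 patients in complete cycles, or 27–36 with the half cycle pro rata. Both lie wholly below 40 to 50. Counting the unfinished fifth cycle as a full group gives 30–40, which meets the target only at its lower edge. At 8 to 10 per cycle the picture is less clear, and the ceiling of 15 leaves the target attainable.

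This is a moderate error of consistency and feasibility that should be fixed. It is not a loss of power.

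**What to change.** - Reconcile the weekly rotation and the three-Thursday statement in the Timeline paragraph with each other, and both with the six cycles under Population.
- Reconcile 6 to 8 (Population) with 8 to 10 (Data Collection), and say whether the latter is per cycle or for the whole study.
- Restate the number of cycles and the expected interview total from the figures kept, showing the multiplication.
- Say whether patients in a partial cycle count towards the total, and whether a patient can count in more than one cycle.

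Which schedule or group size to keep is for the study team to decide; this review proposes neither. The change is to Protocol wording only and requires no extra enrolment. Its one cost is that the restated interview total may be less favourable than 40 to 50.

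### Does it matter that the protocol names two different pairs of clinicians as recruiters for the interviews?

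*Protocol*

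**What the plan says.** The protocol deals with recruitment in two neighbouring paragraphs.

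- **Recruitment.** Patients are first asked for permission to be contacted: "Using the Patient Recruitment Script postcard we will seek permission to contact persons to participate in interviews". Two people then sound them out: "The psychosocial obstetrician and the perinatal psychiatrist will engage potential patients to identify if they might have an interest". Screening is given to the clinicians as a group: "Our team of clinicians will screen patients prior to any initiation of engagement".
- **IPPC team composition.** Five roles are listed: psychosocial obstetrician, midwife clinician scientist, perinatal psychiatrist, Elder and Social Work. The paragraph closes with a restriction, "Only the Psychosocial Obstetrician and the midwife clinician scientist, however, will be involved in the recruitment", and gives its reason: "as they have the primary relationship with all IPPCC patients".

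Two other places bear on the point. The background text before Hypothesis and Outcomes says who runs the sessions: "The team members from the interprofessional team who will guide the sessions are, Psychiatry-lead, Social Work, and Elder". Data Analysis says who handles the transcripts: "We will all code the data and come together to cross-check and validate our interpretations".

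**The concern.** Taken literally, the two paragraphs cannot both be followed. The first gives the psychiatrist a part in recruitment. The second excludes every role except the obstetrician and the midwife, and the psychiatrist and midwife are listed as separate members of the team.

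The possible consequence is more than editorial. The interviews are meant to show how patients experienced the DBT skills sessions, and psychiatry is named as leading those sessions. If the person who leads the sessions also invites patients to be interviewed about them, some may find it harder to decline or to be critical. The protocol itself describes a population facing stigma, fear of child apprehension and unequal power in care, so who asks is a fair question. At stake would be the voluntariness of participation and the candour of the only patient data that the study collects.

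**Working it through.** No formula applies and the protocol gives no figure to reproduce. The check is to compare the two lists, look for text that reconciles them, and ask what would differ under each.

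**Step 1: compare the lists.** List A (Recruitment) is {obstetrician, psychiatrist}. List B (team composition) is {obstetrician, midwife}. They have 1 member in common out of 2. Because list B is worded as exclusive, the conflict over the psychiatrist is genuine.

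**Step 2: look for a reconciling reading.** The restriction refers to recruitment through the project's patient-engagement activities, so one might read list A as an early sounding-out and list B as recruitment proper. That does not work. List A stands under the Recruitment heading and concerns interest in the interviews, and Data Collection names those interviews as one of the two methods of engagement. No section separates a first approach from a later recruitment step.

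**Step 3: ask whether one list carries less pressure.** The five roles less the three disciplines that guide the sessions (psychiatry, Social Work, Elder) leave 5 − 3 = 2, and those two are list B. That makes list B look cleaner, but the comparison depends on what is counted:

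| Recruiters who are… | List A | List B |
|---|---|---|
| from a discipline that guides the sessions | 1 of 2 | 0 of 2 |
| said to hold the primary relationship with all clinic patients | 1 of 2 | 2 of 2 |
| apparently the project's own lead | 0 of 2 | 1 of 2 |
| members of the treating team | 2 of 2 | 2 of 2 |

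Two entries rest on inference. In the first row, the protocol names psychiatry as session lead without saying that the lead is the perinatal psychiatrist. In the third row, the opening background is written in the first person by a clinician midwife, which suggests, without proving, that the midwife clinician scientist is the project lead. List A does better on two rows, list B on one, and they tie on the last. These counts are not effect sizes. They show only that no ordering of the lists by pressure follows from the text.

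**Step 4: ask what else differs between the lists.** Screening by the team of clinicians, the scripted postcard, the neutral interview space at the hospital (Data Collection), coding by the whole team and patients' review of transcripts and analysis (Data Analysis), and coded recordings (Privacy) are the same under both. What patients are willing to say depends at least as much on who interviews and who codes as on who invites, and neither recruitment sentence touches those. The planned numbers and the content analysis do not depend on the recruiter.

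**The case for a change.** The strongest argument for an amendment is that the contradiction needs no inference. Both sentences are intact and current, one is exclusive, and who invites participants is properly a protocol matter. Correcting one sentence would cost almost nothing. The restriction is also the only one of the two statements that comes with a reason, so aligning the Recruitment paragraph with it looks natural, and it would take the session-leading discipline out of the invitation.

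The first part stands: the text is inconsistent and should be tidied up. The second part does not carry the weight placed on it. The restriction and its reason favour the obstetrician and midwife but do not prove that this pair was intended. Replacing the psychiatrist with the midwife would remove one possible source of pressure and bring in two others, a recruiter with the primary relationship to the patients and the apparent project lead. It would also lose the psychiatrist's contacts as a route of invitation. Nor would staff be left without guidance, since the later sentence is explicit.

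**Conclusion.** The inconsistency is confirmed, but it is a clerical slip that calls for no change to the plan. It concerns one name in a two-person list, in a single clinic with five team roles. Its effect on consent or candour cannot be quantified from the protocol, and the text shows no net reduction in pressure or bias from choosing either list. No sample size, outcome, analysis or conclusion is affected.

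This rests on two assumptions. The first is that screening, invitation and coding stay within the treating team, as the protocol states. The second is that inviting and interviewing are separate tasks; had the protocol made the recruiter also the interviewer, the identity of the recruiter would matter more. At the next routine revision the sponsor can state one list and use it in both paragraphs. Which list was intended is for the sponsor to say.
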